6.8. Screening, assessments and follow-up (Table 6.3.)

Potential participants are screened by telephone interviews to assess the main inclusion/exclusion criteria. Those who qualify are invited for the first screening visit during which a brief informed consent is obtained and the 4 m walk at usual pace is administered. Blood level of IL-6 is tested in those with a walking speed <1 m/sec and >0.44 m/sec. Participants with qualifying IL-6 levels are invited for the second screening visit to review medical history and current medications, complete blood testing (vitamin D, CBC, chemical panel, and second IL-6 measure), vital signs (blood pressure, pulse and temperature), 400 m walk, and the Mini Mental State Examination (MMSE).¹⁸⁵ The study medical safety officer will review the participant's health history, medication use, vital signs, and laboratory test results, and clear for randomization according to the study inclusion and exclusion criteria. If there are no safety concerns, participants attend the baseline visit during which the following is completed: full informed consent, questions to assess frailty,¹⁷¹ blood collection for labs, vital signs and anthropometric measurements, the SPPB, isokinetic dynamometry of the knee extensors and flexors, grip strength, and questionnaires. Validated Minnesota physical activity¹⁸⁶, depressive symptoms (CES-D)¹⁷⁵, patient reported outcomes (SF-36), and fatigability¹⁹⁸ questionnaires are completed at the baseline and 12 month visit. The physical activity results are used as potential modifiers in the data analyses. If there are no exclusion criteria identified, the participants are randomized, and the study drugs are dispensed. The baseline measures are repeated as outlined in Table 6.3. BP&P, blood tests and adverse events are measured about 1 week after randomization and after each visit when the LO dose is modified. Medication dose is adjusted as outlined in the above titration and safety algorithms.

6.9. Measure of additional biomarkers Inflammation, characterized by higher blood cytokine levels related to the activation of innate immunity and other systems (coagulation), is part of the aging process, plays a role in virtually all diseases, and contributes to mobility limitations.¹ While it is known that inflammation markers predict these outcomes and mortality, little is known about how anti-inflammatory interventions affect the plasma cytokine levels, or associated pathways. Thus, we measure novel and established markers of inflammation and aging at baseline, and follow-up, and relate these to both change in IL-6 and change in walking speed to:

(1) Characterize the effect of the interventions on these cytokines: (1.a.) Are these cytokines/pathways impacted by the interventions? (1.b) Are the changes in these markers pre- vs. post-intervention less than, equivalent to, or greater than that of IL-6?

(2) Assess if these biomarkers yield independent information from IL-6 with respect to the change in walking speed and/or provide benefit for screening participants in the main ENRGISE trial.

6.10 Data analyses and power for the ENRGISE Pilot Study and biomarkers assays

The data analyses and power section is presented in the order by which the aims are likely to be achieved rather than the order in which the aims are stated elsewhere in the protocol.

6.10.a. Feasibility and recruitment

Feasibility of recruitment and identifying the study population are contained in Aim a (ii). In the ENRGISE Pilot Study we will use one-sided tests/confidence intervals because we wish to rule out conditions that would make the main study infeasible. Having a higher than hypothesized safe tolerable rate, higher yield for recruitment, or stronger relationship between the changes in IL-6 and walking speed would simply make the follow-up study easier to implement. For efficacy, we use tests at the 10% significance level;^{187, 188} this is consistent with the FDA's aims for phase 2 versus phase 3 studies.^{189, 190} No formal adjustment for multiple comparisons is planned for the pilot study.

We assess the recruitment yields in strata 1-3 presented in Table 6.1 and the proportions of people who tolerate LO and ω -3. One-sided exact confidence intervals of these proportions are calculated. If we need to screen 300 people to recruit 75 into strata 1 (People not using ω -3) or 2 (People not using ACEI or ARB) (25% yield), the 95% one-sided CI would set the lower bound of our recruitment yield at 20.9% using a Clopper-Pearson interval¹⁹¹ and 8.3% if we need to screen 750 (10% yield). For stratum 3 (People not using ACEI, ARB, or ω -3) (target 150), these lower limits would be 22.1% (25% yield) or 8.8% (10% yield). Note that those eligible for stratum 3 are also eligible for strata 1 and 2; these people are also used to estimate the

proportions eligible; thus, our CIs above are conservative.

6.10.b. Intervention Effect

We use the "intention to treat" approach assuming participants are grouped according to randomization for all analyses of the intervention effect. The stratified recruitment and randomization allow us to compare mean log(IL-6) between each of the three active groups to placebo using a linear mixed model with both main effects and their interaction, adjusted for baseline log(IL-6) and strata. Time is a repeated factor, and the primary comparison is based on a contrast at 12 months. The covariance structure will be assumed to be unstructured. The primary focus is on marginal comparisons (135 and 165/group) between each active intervention and placebo using one-sided hypothesis tests at the 10% level (we are not looking for definitive evidence, but to rule out small effects). We assume 5% loss to follow-up (LTFU); this is similar to the 5% we achieved in LIFE. Using the root mean squared error from LIFE-P (adjusted for baseline log(IL-6) and treatment) of 0.52, we have 91% power to detect a difference if the difference (on the log scale) is at least 0.1625. This is equivalent to the difference between 4.20 and 3.57 pg/ml (or a 15% difference). We would have 66% power for a 10% difference (4.20 vs. 3.78 pg/ml, 0.1054 on the log scale) and 99% power for a 20% difference (4.20 vs. 3.36 pg/ml, 0.2231 on the log scale). Individual treatment group comparisons (at least 60 vs. 75/group) would have 44% power for a 10% difference, 68% power for a 15% difference, and 87% power for a 20% difference. This achieves the first part of Aim a (i). As sensitivity analyses, we also explore the impact of additional factors (e.g., diet, physical activity, medication use) by adding these factors to the models. Although the mixed model is robust against data missing at random (MAR), multiple imputation will be used in sensitivity analyses.

From LIFE-Pilot, the SD of 400 m walk speed in IL-6 eligible participants is 0.21 m/s, with high correlation ($r > 0.80$) between baseline and 12 month measures. With at least 60 and 75 participants per group (for pairwise comparisons), we project to have >99% power to detect a difference in means of >0.095 m/sec using a one-sided test at the 10% level (a substantial meaningful change).¹⁹² There is also 67% power to detect a >0.038 m/sec difference (a small meaningful change). Using groups of 135 and 165 (for main effects), we would have >99% power to detect >0.095 m/sec, and 86% power for a difference >0.038 m/sec in walking speed. This analysis uses linear mixed models, as for IL-6; a similar approach is used for the secondary outcomes of SPPB, frailty, and grip strength. This achieves the last part of Aim a (i). For people who are unable to complete the 400m walk, we will use their walking speed from the portion completed.

6.10.c. Associations between inflammation and function

We base our calculation of detectable SPPB effects on LIFE data. The correlations between baseline and 24 month follow-up SPPB outcomes were 0.49 (Successful Aging: SA) and 0.47 (Physical Activity: PA); we assume a correlation of 0.5 between baseline and 12 month in ENRGISE. Estimated standard deviations at 24 months were 2.60 (SA) and 2.47 (PA); we assume 2.5. Under these assumptions, for the comparisons of 60 to 65 people, we have 90% power to detect a difference of at least 0.99 SPPB units; for the comparisons of 135 to 165 people, we have 90% power to detect a difference of at least 0.66 SPPB units. Both assume 1-sided tests at the 10% level.

We will examine the relationship between the change in IL-6 and the change in walking speed using univariate regression. Assuming we assess ≥ 285 participants (of 300, $\geq 95\%$) at 12 months, we have 80% power to detect a correlation less than -0.126 (i.e. at least 1.59% of explained variability) using a one-sided test at the 10% level. We have 90% power if the correlation is less than -0.152 (Aim a (iii)).

To assess intra-person variability in IL-6 (Aim a (iii)), we measure IL-6 at both screening visits. We use a Bland-Altman plot to assess agreement; this is summarized using a 95% CI of the difference at the two visits providing information on the expected differences over one week due to biological variability and measurement error. If agreement is high, one measure is likely sufficient for recruitment into the main study. If not, we may need to use two or more measures to determine eligibility and to assess participant-specific risk.

6.10.d. Additional inflammatory biomarkers:

In addition to IL-6 levels, we examine additional markers of inflammation (Aim b (i) and (ii)). As with IL-6, our primary focus is on the relationships between changes in cytokines with the change in walking speed using linear mixed models. We use stratified linear mixed models (as described above for IL-6) to examine the impact of interventions on these cytokines. These analyses assess whether changes in these cytokines are of similar magnitude to IL-6. As the absolute levels differ between cytokines, focus is on relative changes from baseline. We also examine these cytokines in models also including baseline and follow-up log(IL-6) to assess whether they provide additional predictive information. We also explore MMD event rates by baseline levels of IL-6 and additional cytokines to explore whether we can use an additional cytokine to select a population at greater risk to use for the main study, recognizing the potential tradeoff between ease of recruitment and selecting a population at higher risk.

6.10.e. Informing the main study

We assess compliance and retention rates (Aim a (ii)). Although we expect to be underpowered for incident mobility disability, we collect these data and compare estimates of event rates to those obtained in SA group LIFE participants that would have been eligible for ENRGISE (Aim a (ii)). While power is limited, we also examine whether there is sub-additivity and interaction of interventions in stratum 3, which supports the decision of whether to proceed with a factorial or parallel group design in Phase 3 (Aim a (ii)). .

We integrate all available information to make a determination about which approaches to carry forward into the main study. Weighed in this decision is recruitment yield (is it practical to consider a full size trial?), safety and tolerability (do participants tolerate the interventions?), changes in IL-6 in the pilot studies, the relationship of change in IL-6 with change in walking speed, the conclusions from our data analysis of other studies (e.g. LIFE, Look AHEAD, Health ABC, CLIP), and a revised literature search. Finally, we combine all information to estimate the sample size and **cost of the main trial** (Aim a (ii)). For example, for a two-arm study, we would need 2,084 people to have 90% power to detect a 20% (HR=0.8) reduction in MMD assuming a two-sided test at the 5% level, a control group event rate of 18.3%/year, LTFU of 5%/year, 18 months of recruitment, and a total study length of 4 years. To detect a 25% effect (HR=0.75), we would need 1,296 people. These calculations use the estimated MMD rate of 18.3%/year in the control group among people in LIFE-P whose baseline IL-6 was between 2.5 and 10 pg/ml.

7. Possible Discomforts and Risks**7.1. Confidentiality**

Lack of maintenance of confidentiality is a potential risk. The information below relates to all collaborating performance sites for the proposed study. Data are used only in aggregate and no identifying characteristics of individuals will be published or presented. Results of testing are sent to participant's private physicians if participants agree to this. Alert values for medically relevant procedures (e.g., blood pressure, pulse rate, MMSE, blood tests) are sent to participants and participants' physicians, depending on the urgency of the values.

Confidentiality of data is maintained by using research identification numbers that uniquely identify each individual. Safeguards are established to ensure the security and privacy of participants' study records. Appropriate measures are taken to prevent unauthorized use of study information. The research ID number is used. The research records are kept in a locked room in the Field Center. The files matching participants' names and demographic information with research ID numbers are kept in a locked file. Only trained and certified study personnel has access to these files. After the study is completed, local data are stored with other completed research studies in a secured storage area.

In compliance with the Health Insurance Portability and Accountability Act (**HIPAA**) and the Standards for Privacy of Individually Identifiable Health Information of the Department of Health and Human Services, we access personal health information and medical records only after receiving signed informed consent.

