additional biomarkers, their relationship with walking speed and their impact on recruitment and effect size estimates; and (10) estimate the cost of the main trial.

Table 6.1. Randomization strata according to medication use at baseline – Total N=300

Strata according to medication use at baseline	LIFE N (%) Observed	ENRGISE pilot N (%) Proposed	Randomization weights			
			Placebo LO Placebo ω-3	LO Placebo ω-3	Placebo LO ω-3	LO ω-3
1 No ω-3 (ACEI/ARB ok)	637 (44.1)	75 (25%)	0.4*	0	0.6*	0
2 No ACEI/ARB (ω-3 ok)	154 (10.7)	75 (25%)	0.4**	0.6**	0	0
3 No ACEI/ARB, No ω-3	655 (45.3)	150 (50%)	0.2	0.2	0.2	0.4
Overall		300 (100%)	0.3 (n=90)	0.25 (75)	0.25 (75)	0.2 (60)

* Does not receive placebo LO, and ** does not receive placebo ω-3 as the use of the corresponding drugs is permitted at baseline

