Recruitment is planned to last 1 year and each participant is being followed for 1 year. To assess recruitment yields according to different targets, we stratify on ACEI/ARB and baseline ω-3 use. The first stratum (people not using ω-3) is randomized to placebo or ω-3. The second stratum (people not using ACEI or ARB) is randomized to placebo or LO. The third stratum (people not using ACEI, ARB, or ω-3) is randomized to placebo, LO, ω-3, or the combination. The original ENRGISE targets, based on the estimated proportions in LIFE are presented in Table 6.1. (We note that during the ENRGISE DSMB’s August 23, 2016 phone call, the DSMB approved the investigators’ request to lift the upper limit on the number recruited into stratum 1. In the text which follows, the original sample sizes remain as we do not know how many we will recruit into each stratum. The randomization weights will remain unchanged.) We expect to have a slight imbalance in the overall numbers within each treatment group of 90, 75, 75, and 60. Oversampling of the control group allows us to better estimate parameters associated with IL-6, walking speed, and major mobility disability in that group; this is important for planning the sample-size of the main trial. Note that anybody eligible for stratum 3 is also eligible for strata 1 and 2. To achieve overall balance between the two single interventions, we focus attention on having equal numbers in strata 1 and 2 but do not worry if either is less than 25% of the total as randomizing additional people in strata 3 provides similar information. If 20% were in each of strata 1 and 2, the overall weights would be 0.28, 0.24, 0.24, and 0.24; if 15%, then 0.26, 0.23, 0.23, and 0.28. Both are close to Table 6.1. and do not markedly reduce power for any comparison.

6.2. Interventions and compliance. .

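### The marginal IL-6 power (66/91/99%) and SPPB difference (0.66) count, for each drug, 75 people in a stratum where nobody can receive it; under the strata-adjusted model they are about 56/82/96% and 0.79

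*Combined protocol and SAP*

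**What the plan says.** Section 6.1 and Table 6.1 set out three strata with different randomisations. "The first stratum (people not using ω-3) is randomized to placebo or ω-3". Nobody in that stratum can be allocated losartan. Stratum 2 is the mirror image, where only losartan and its control are available; only stratum 3 is randomised to all four arms. The planned sizes are 75, 75 and 150. Section 6.1 also reports that the cap on stratum 1 was lifted, and that in the text "the original sample sizes remain as we do not know how many we will recruit into each stratum".

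Section 6.10.b compares mean log(IL-6) "using a linear mixed model with both main effects and their interaction, adjusted for baseline log(IL-6) and strata". It then says: "The primary focus is on marginal comparisons (135 and 165/group) between each active intervention and placebo", with one-sided tests at the 10% level and 5% loss to follow-up. The residual SD is introduced with "Using the root mean squared error from LIFE-P (adjusted for baseline log(IL-6) and treatment) of 0.52". From these come 66%, 91% and 99% marginal power for 10%, 15% and 20% differences. For pairs of arms: "Individual treatment group comparisons (at least 60 vs. 75/group) would have 44% power for a 10% difference", followed by 68% and 87% for 15% and 20%.

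The same section says that SPPB is analysed in a similar way to IL-6. Section 6.10.c uses 135 and 165 again to give 0.66 SPPB units at 90% power.

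**The concern.** The power calculation and the analysis model do not describe the same comparison. The 165 people not on losartan are 30 in stratum 2, 60 in stratum 3 and all 75 of stratum 1. Once each stratum has its own intercept, stratum 1 contains no losartan contrast, so its 75 people cannot inform the losartan effect directly. The same is true of ω-3 and stratum 2.

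This affects the comparison that the plan calls its primary focus, and the plan says that the purpose of the test is to exclude small effects. Overstated power for small effects would make a null marginal result look more informative than it is when the investigators decide whether one or two interventions go forward.

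**Working it through.** **Inputs.** Table 6.1 cells: stratum 1, placebo 30 and ω-3 45; stratum 2, placebo 30 and losartan 45; stratum 3, placebo 30, losartan 30, ω-3 30 and combination 60. Section 6.10.b: residual SD 0.52; log-scale differences 0.1054, 0.1625 and 0.2231; one-sided 10% (z = 1.2816); 5% loss. Section 6.10.c: SPPB SD 2.5 and baseline correlation 0.5.

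**Formulas** (normal approximation). Effective size n_eff = n1·n2/(n1 + n2), or its equivalent from the inverse of the weighted design matrix. Power = Φ(d·√n_eff/0.52 − 1.2816). SPPB difference at 90% power = 2 × 1.2816 × 2.5 × √0.75/√n_eff.

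**The plan's own figures.** 0.95 × 135 × 165/300 = 70.5. This gives 66.3%, 91.0% and 99.0%, and an SPPB difference of 0.661. All four stated figures are reproduced. Adding both drugs and their interaction, still without strata, gives n_eff 69.8 and 66.0/90.8/98.9%. So the drug terms do not cause the gap.

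**With strata, one drug, by hand.** For losartan, stratum 1 contributes 0, stratum 2 contributes 45 × 30/75 = 18, and stratum 3 contributes 90 × 60/150 = 36. The total is 54, and 0.95 × 54 = 51.3. This equals a comparison of 135 with 90.

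**With strata, full model.** The design is symmetric, so losartan and ω-3 give the same values. With the interaction in the model, the marginal effect is averaged equally over the two levels of the other drug.

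| Model (5% loss) | n_eff | 10% / 15% / 20% | SPPB |
|---|---|---|---|
| 135 vs 165, no strata | 70.5 | 66.3 / 91.0 / 99.0 | 0.66 |
| Strata + one drug | 51.3 | 56.8 / 83.1 / 96.3 | 0.775 |
| Strata + both drugs | 50.7 | 56.4 / 82.7 / 96.2 | 0.78 |
| Strata + both drugs + interaction (as planned) | 49.1 | 55.5 / 81.8 / 95.8 | 0.79 |

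The IL-6 difference detectable with 91% power becomes 0.192 to 0.195 on the log scale (17 to 18%), against the stated 0.1625 (15%). Power for 0.66 SPPB units is 80 to 81%, not 90%.

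**Pairs of arms, planned model.** Single drug vs placebo: n_eff 33.6, power 46/70/89%, so the stated minimum of 44/68/87% holds. Combination vs placebo: n_eff 26.6, power 41/63/82%, which is below it. The combination is given only in stratum 3. The 41/63/82% borrows from the single-drug contrasts in strata 1 and 2, on the assumption that drug effects are equal across strata. Stratum 3 alone (28.5 vs 57 after loss, n_eff 19.0) gives 34.5/53.2/72.2%.

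**Sensitivity at a 15% difference.**
- With no loss at all, power is 83 to 84%.
- Section 6.1's own alternative mixes, with 20% or 15% of participants in each of strata 1 and 2, give 84% and 86%.
- Restoring 91% would need a residual SD of 0.434 to 0.441. Strata would then have to explain 28 to 30% of the residual variance 0.52².

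**The case against.** The strongest reply is that this is a pilot that does not seek definitive evidence. Section 6.10.e makes the IL-6 change one of several inputs, and no decision rule hangs on the test. The effects that the plan cites for these drug classes exceed 40%, and power at 40% is above 99.9% even with fixed strata. This stands as a limit on the consequences. It does not answer the plan's own stated interest in small effects, which is where the loss falls.

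A second reply is that the corrected figures rest on two things the documents do not state: that strata enter as fixed effects, and that the residual SD stays at 0.52 after adjustment for them. That is fair, and both conditions must accompany the numbers. Neither rescues the stated 91%. With random stratum effects and an assumed between-stratum SD of 0.02 to 0.20 on the log scale, power for a 15% difference runs from 90% down to 83%. Nothing in the documents suggests that strata explain the 28 to 30% of residual variance required.

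Third, the stratum sizes are provisional now that the stratum 1 cap is lifted. This is true, but it does not favour the plan. If the total stays at 300 and the mix were 150/50/100 (an illustrative assumption), the planned model would give about 70% for losartan and 78% for ω-3 at a 15% difference.

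**Conclusion.** The concern holds. The stated marginal figures come from a comparison without strata, whereas the plan specifies a strata-adjusted model. With strata as fixed effects, residual SD 0.52, 5% loss, a one-sided 10% test and the Table 6.1 sizes, marginal IL-6 power is about 56%, 82% and 96%, and the SPPB difference is about 0.79. Under those assumptions the chance of missing a true 10% reduction is about 44%, not 34%. Every fixed-strata variant with 5% loss lies within 2 percentage points and 0.02 SPPB units of these values.

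The single-drug pairwise IL-6 figures are sound; the combination falls slightly short of them. The analysis and its type I error are unaffected. No error is claimed for walking speed. Section 6.10.b gives only a correlation above 0.80, and with fixed strata power at 0.038 m/s is about 80 to 81% at r = 0.80 and 85 to 86% at r = 0.84. The stated 86% is therefore compatible with the text.

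**What to change.** Replace the marginal and pairwise power text in Sections 6.10.b and 6.10.c along these lines:

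*With strata as fixed effects, a residual SD of 0.52 carried over from LIFE-P (not adjusted for strata), 5% loss, a one-sided 10% test and the Table 6.1 sizes, marginal power for IL-6 is about 56%, 82% and 96% for differences of 10%, 15% and 20%. Single drug vs placebo has at least 44%, 68% and 87%. Combination vs placebo has about 41%, 63% and 82%, assuming drug effects are equal across strata. The marginal SPPB difference detectable with 90% power is about 0.79.*

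Add that strata 2 and 3 inform the losartan contrast and strata 1 and 3 the ω-3 contrast. Also add that losartan power falls further if extra stratum 1 recruitment displaces strata 2 and 3, and that ω-3 power can fall too if stratum 3 shrinks. For consistency, check the pairwise SPPB figure of 0.99 as well: on n_eff 26.6, combination vs placebo needs about 1.08. For walking speed, it is enough to state the correlation and model behind the 86%.

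The cost is wording only. The printed figures become less favourable; enrolment, randomisation and analysis do not change.

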To address this gap in evidence, we will conduct the main randomized clinical trial (RCT) **ENRGISE (ENabling Reduction of low-Grade Inflammation in SENiors)** to test the ability of anti-inflammatory interventions for improving or preserving walking ability. We have maximized the public health impact of the interventions by selecting interventions that are safe, tolerable, acceptable, and affordable for vulnerable older persons. Based on an extensive literature review, we test the efficacy of the angiotensin receptor blocker (ARB) losartan (LO) and omega-3 polyunsaturated fatty acids (ω -3) as fish oil. To maximize the anti-inflammatory effect and potential benefit on mobility, we explore both individual and combination interventions that target different, but complementary and potentially synergistic anti-inflammatory mechanisms.¹²⁻¹⁵ We plan to recruit older persons at risk for, or with, mobility impairment, as measured by slow gait speed and self-reported mobility difficulty, and who have elevated blood levels of IL-6 (>2.5 pg/ml), the marker most consistently associated with mobility limitations.¹⁻⁷ Preliminary data on feasibility and information required for obtaining sample size estimates are needed to effectively design and implement the main trial. Thus, we implement the following **specific aims** for the ENRGISE Pilot Study:

- a. Conduct a pilot RCT in 300 older persons at risk of mobility decline to assess: (i) compared with placebo, the effects of LO, ω -3, and LO+ ω -3 on IL-6 and walking speed; (ii) the recruitment yields, the target population, adherence, retention, tolerability, sample-size, design, and cost for the main RCT; and (iii) the intra-subject variability of IL-6, and the dosage and safety of the interventions.
- b. Measure novel and established inflammatory markers to:
 - i. Characterize the effect of LO and ω -3 on these biomarkers and determine: (a) Are these cytokines/pathways impacted by the interventions? (b) Are the changes in these markers pre- vs. post-intervention less than, equivalent to, or greater than that of IL-6? and
 - ii. Assess if these biomarkers yield independent information from IL-6 with respect to change in walking speed and/or provide benefit for screening participants for the main trial.

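### The single pairwise power floor in section 6.10.b holds for each drug alone against placebo at the Table 6.1 allocation, but not for the combination

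*Combined protocol and SAP*

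**What the plan says.** Aim a (i) in section 4 is to assess, "compared with placebo, the effects of LO, ω -3, and LO+ ω -3 on IL-6 and walking speed". Section 6.10.b sets out the analysis: "compare mean log(IL-6) between each of the three active groups to placebo using a linear mixed model with both main effects and their interaction". That model is also "adjusted for baseline log(IL-6) and strata", with the contrast taken at 12 months. After the power for the marginal comparisons (135 and 165), the section gives the pairwise power: "Individual treatment group comparisons (at least 60 vs. 75/group) would have 44% power for a 10% difference, 68% power for a 15% difference". For a 20% difference the stated power is 87%. The next sentence says this meets the first part of Aim a (i). The text does not say which two groups the 60 and 75 are.

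The next paragraph uses the same 60 and 75 for pairwise comparisons of 400 m walking speed: over 99% power for 0.095 m/s and 67% for 0.038 m/s. Section 6.10.c gives a 90%-power detectable SPPB difference of 0.99 units for 60 against 65.

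On allocation, section 6.1 says: "We expect to have a slight imbalance in the overall numbers within each treatment group of 90, 75, 75, and 60". Table 6.1 gives the combination zero weight in strata 1 and 2. It is available only in the third: "The third stratum (people not using ACEI, ARB, or ω-3) is randomized to placebo, LO, ω-3, or the combination". Section 6.1 also reports that the DSMB approved the investigators' "request to lift the upper limit on the number recruited into stratum 1", so final stratum sizes are unknown and the original sizes are kept in the text. The randomisation weights do not change.

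**The concern.** A figure worded as a minimum, placed after a sentence naming all three active groups and credited to an aim that names the combination, reads as a floor for the combination too. Yet all 60 combination participants are in stratum 3, with only 30 of the 90 placebo participants. The other 60 placebo participants are in strata 1 and 2, where nobody receives the combination. Once strata are in the model, they inform the combination contrast only indirectly.

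Section 6.1 says that the pilot is to support the choice between one and two interventions and, if two, between a three-arm and a factorial main trial. How informative the combination arm will be bears on that choice, so its power should be stated correctly. The limited-power caveat in section 6.10.e concerns sub-additivity and interaction in stratum 3, not combination against placebo.

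**Working it through.** **Inputs.** From 6.10.b: one-sided 10% level (z = 1.2816), residual SD 0.52 on log(IL-6), 5% loss to follow-up, and differences d of 0.1054, 0.1625 and 0.2231 for 10, 15 and 20%. From Table 6.1 (placebo/losartan/ω-3/combination):
- stratum 1: 30/0/45/0
- stratum 2: 30/45/0/0
- stratum 3: 30/30/30/60

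**Formula.** Power = Φ(d·√(0.95·I)/0.52 − 1.2816). For a simple two-group comparison, I = n₁n₂/(n₁+n₂).

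**The plan's own figure.** For 60 vs 75, I = 4500/135 = 33.3. Power is 44.4/68.3/87.1%, which reproduces the stated 44/68/87%.

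**Combination under the planned model** (strata, both drugs, interaction; each drug's effect equal across strata). Stratum 1 estimates the ω-3 effect with information 30×45/75 = 18, and stratum 2 does the same for losartan. Through these, each single-agent group of 30 in stratum 3 adds 30×18/48 = 11.25 placebo-equivalents. The effective placebo group is 30 + 11.25 + 11.25 = 52.5, so I = 60×52.5/112.5 = 28.0.

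**Single agent under the same model.** I = 18 from its own stratum, plus 30×41.25/71.25 = 17.4 from stratum 3 (41.25 = 30 + 11.25), which makes 35.4.

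**Stratum 3 alone**, with no assumption across strata: I = 60×30/90 = 20.0.

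| IL-6 comparison with placebo, Table 6.1 | I | 10% | 15% | 20% |
|---|---|---|---|---|
| Stated (60 vs 75) | 33.3 | 44 | 68 | 87 |
| Losartan or ω-3 alone, planned model | 35.4 | 46 | 70 | 89 |
| Combination, planned model | 28.0 | 41 | 63 | 82 |
| Combination, stratum 3 alone | 20.0 | 35 | 53 | 72 |

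The overall head count for the combination, 60 vs 90 (I = 36.0), would give 46/71/89%. It does not apply to a strata-adjusted contrast.

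**Other stratum mixes (N = 300), combination, planned model.**
- 20/20/60: I = 31.7, power 43/67/86%.
- 15/15/70: I = 34.7, power 45/70/88%.
- Larger stratum 1, if the LIFE proportions in Table 6.1 recurred (about 132/32/136): 39/60/80%. Losartan alone would then have 38/59/78%.
- Larger stratum 1, assumed 120/60/120: 37/58/77%. Losartan alone would then have 41/64/83%.

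The last two mixes are illustrations only; the documents give no final sizes.

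**Walking speed.** With r = 0.80, the residual SD is 0.21×√(1−0.64) = 0.126. At 0.038 m/s, 60 vs 75 gives 66% with 5% loss to follow-up and 68% without (67% stated). The combination gives 61% and 62%. At 0.095 m/s the combination has 99.5%, so the claim of over 99% stands.

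**SPPB.** The residual SD is 2.5×√0.75 = 2.165, and the difference detectable with 90% power is 2×1.2816×2.165/√(0.95·I). The combination gives 1.08. The stated 0.99 comes from 60 vs 75 with loss to follow-up (0.986) or from 60 vs 65 without it (0.993). For 60 vs 65 with loss to follow-up it is 1.02.

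**The case against.** A reader might infer that the power section ignored the strata altogether. The documents do not support that. In the strata that offer a given drug, placebo against that drug alone is 30+30 = 60 against 45+30 = 75, exactly the stated count. The figure may therefore be a strata-aware one for single agents, and for them it is slightly conservative. What is missing is a figure for the combination.

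A reader might also infer that the dependence on stratum sizes is hidden. It is not: section 6.1 says the sizes are unknown and works through 20/20/60 and 15/15/70. The results above agree with its statement that neither mix markedly reduces power. Both alternatives shrink strata 1 and 2, however, and neither covers the larger stratum 1 that lifting the cap permits.

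The SD of 0.52 was adjusted for baseline and treatment, not strata. An SD of about 0.477 (0.52×√(28.0/33.3)), 8% lower, would close the IL-6 gap. The documents give no strata-adjusted value, and the plan's own power uses 0.52.

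The walking-speed shortfall is less certain. The plan says r exceeds 0.80, and at r = 0.84 the combination reaches the stated 67%. At r = 0.80 the plan's 86% for 135 vs 165 does not reproduce either (about 90%), so its exact inputs are unclear.

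Finally, the pairwise comparisons are not the primary focus, the pilot does not seek definitive evidence, and the decision in 6.10.e weighs many inputs with no power threshold. All of this stands and limits the consequence. It does not make the stated minimum right for the combination.

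**Conclusion.** The point holds for the combination at the Table 6.1 allocation: about 41/63/82% power for 10/15/20% IL-6 differences, against the stated minimum of 44/68/87%. That rests on SD 0.52, 5% loss to follow-up, no gain from earlier visits, and drug effects equal across strata, which the plan does not state. Without that last assumption, stratum 3 alone gives 35/53/72%. For losartan alone or ω-3 alone the stated figures hold at Table 6.1.

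The shortfall of 3 to 5 points is modest. It is about 2 points or less at 20/20/60, absent at 15/15/70, and larger if stratum 1 grows at the expense of stratum 3. Confidence is high for IL-6 and lower for walking speed, which depends on r. It would be wrong to conclude from this that the pairwise figures fail generally or that the planned analysis is unsound. The primary marginal comparisons (135 vs 165) are outside this point.

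**What to change.** In section 6.10.b, state that the 60 vs 75 figures for IL-6 and walking speed apply to single agent against placebo at the Table 6.1 allocation. Then add, for combination against placebo (randomised only in stratum 3, 60 vs 30):

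- **IL-6:** about 41/63/82% power for 10/15/20% differences under the planned model, assuming equal drug effects across strata; 35/53/72% from stratum 3 alone.
- **Walking speed:** about 61% for 0.038 m/s if r = 0.80, higher if r exceeds 0.80.
- **SPPB (section 6.10.c):** a difference of about 1.08 units detectable with 90% power, with 5% loss to follow-up. Reconcile the 60 to 65 count there with the 60 vs 75 used elsewhere; no Table 6.1 comparison matches 60 vs 65.

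Add that all pairwise figures, single agents included, will be recomputed from the final stratum sizes, because the alternatives in section 6.1 do not cover a larger stratum 1. Do not write an assumed stratum mix into the protocol.

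The cost is a few sentences. The analysis model, sample size and data collection do not change.
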